8.5.1. Post Void Residual (PVR) Urine Volume

Summary statistics will be provided for PVR urine volume and its change from baseline by treatment group (and total for GTC1, GTC2, GTC3 and Overall) and study phases (TC1, GTC1, GTC2 and GTC3) for each visit. Listing will be provided for PVR urine volume and its change from baseline. In addition, the change from baseline in PVR urine volume in TC1 will be analysed using an analysis of covariance (ANCOVA) model as below table.

Summary statistics will be provided for PVR urine volume and its change from baseline in TC1 for age subgroup. See section [5.4.2](#) for details on the subgroup categories.

Proportion of subjects who have a change from baseline in PVR urine volume category will be summarized by treatment group (and total for GTC1, GTC2, GTC3 and Overall)

CONFIDENTIAL

204947

and study phases (TC1, GTC1, TGC2 and GTC3) for each visit. This will also be summarized for the same categories using raw PVR urine volume. The category is:

- < 100 mL
- ≥ 100 mL to < 200 mL
- ≥ 200 mL to < 350 mL
- ≥ 350 mL

For only subjects who used CIC with the reason for urinary retention / elevated PVR, summary statistics will be provided for PVR urine volume at initiating CIC by treatment group in TC1. This value will be PVR urine volume at the time of initiation of CIC (with the reason for urinary retention or elevated PVR) or 2 weeks prior to CIC if not available at the time of initiation.

Note that use of CIC includes use of indwelling catheter, if exists. The reason to use CIC are urinary retention, elevated PVR or other. Only data of use of CIC with the reason for urinary retention or elevated PVR will be used for any analyses, unless otherwise specified.

Listing of PVR data will be produced. This listing will include the following items.

- Site ID, Subject ID, Treatment group, Visit, Date, Study day, PVR value, Flag at initiating CIC (Yes, if the date of PVR is on or at least 2 weeks (14 days) prior to the start date of CIC.)

Study Specific Safety Analyses for PVR volume in first treatment cycle	
Endpoint(s)	

 ● Change from baseline in PVR urine volume in TC1 	
Model Specification	

 ● The endpoints will be analyzed using an analysis of covariance (ANCOVA) model. ● Terms fitted in the ANCOVA model will include: 
 ● Fixed, categorical effects: treatment, site, a stratification factor ● Fixed, continuous effects: baseline value ● The Kenward-Roger option in SAS PROC MIXED will be used to estimate denominator degrees of freedom and standard errors. 	
Model Results Presentation	

 ● Adjusted means (least square means) and corresponding standard errors of means will be presented for each treatment by visit, together with estimated treatment differences (GSK1358820 – Placebo), the corresponding 95% confidence intervals. P-value will not be calculated because p-value is not of interest for safety endpoint in this study. 	

CONFIDENTIAL

204947

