- (e) Urine culture and sensitivity is performed by the central laboratory when urinalysis (dipstick) results were suggestive of a urinary tract infection
- (f) Could be performed during the screening phase excluding diary data collection days
- (g) If the result of urine pregnancy is suspicious, investigator (or sub-investigator) is able to conduct serum pregnancy test by central laboratory.
- (h) First dose to be administered 1 (approximately 24 hours) to 3 days prior to study injection and continued for 1 to 3 days post injection (including the day of injection)
- (i) If qualification for re-treatment criteria was met, the patient will undergo the exams specified in Table 2, column marked "If qualification for re-treatment criteria was met".
- (j) Subjects who are not re-treated will remain in treatment phase 1 and continue to visit at the scheduled study visit.
- (k) Patients must have stopped medication (i.e.: anticholinergic and beta-3 adrenergic receptor agonist indicated for patients with OAB, or other medications) or therapies for OAB for at least 7 days prior to start of screening procedures
- (l) Samples may be collected during the screening period through Day 1 (prior to randomization)

**Table 2 Time and Events Table [Treatment phase 1 (if qualification for re-treatment criteria was met) to treatment phase 2]**

	Treatment phase 1	Treatment phase 2														With drawal
		1st re-treatment	Re-treatment (1st)							If qualification for re-treatment criteria was met (Within 21days prior to re-treatment)	Re-treatment (2nd)					
Week	If qualification for re-treatment criteria was met (Within 21days prior to re-treatment)		2	6	12	18 a	24 a	30 a	Study exit (48 weeks after 1st treatment)		2	6	12 a	18 a	Study exit (48 weeks after 1st treatment)	
Window	0	± 3 d	± 7 d	± 7 d	± 7 d	± 7 d	± 7 d	± 7 d	± 7 d	0	± 3 d	± 7 d	± 7 d	± 7 d	± 7 d	
Patient characteristics etc.																
Neutralizing antibody									X						X	X
Efficacy																
Check of bladder diary b	X		X	X	X	X	X	X	X		X	X	X	X	X	X
KHQ, OABSS	X			X	X	X	X	X	X			X	X	X	X	X
TBS	X		X	X	X		X		X		X	X	X	X	X	X
Safety																
Adverse events	X	X	X	X	X	X	X	X	X	X	X	X	X	X	X	X
Physical exam	X								X						X	X
Height, Weight	X c		X d	X	X	X	X	X	X	X c	X c	X	X	X	X c	X c
Vital signs	X			X	X	X	X	X	X	X	X	X	X	X	X	X

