- b. If a subject does not report any associated symptoms or if they report associated symptoms that, in the opinion of the investigators/subinvestigators, do not require CIC, the subject will be seen at an additional visit 1 week later, when the PVR and any associated symptoms will be reassessed. In addition, a urine analysis with a urine reagent strip as well as urinalysis, urine culture and sensitivity test at the central laboratory will be performed. Based on the test results at this visit, the following procedures will be conducted:
  - 1) If the PVR is increasing and is associated with symptoms, that in the opinion of the investigators/subinvestigators require CIC, then CIC should be initiated and managed according to the Guidance about the Management of PVR Urine Volume.
  - 2) If the PVR is  $\geq 350$  mL then CIC should be initiated and managed according to the Guidance about the Management of PVR Urine Volume.

- 3) If the PVR is increasing but is not associated with symptoms or is associated with symptoms that in the opinion of the investigators/subinvestigators do not require CIC, then the subject will be seen 1 week later to determine if CIC has become warranted based on PVR and/or any associated symptoms. The following procedures will be conducted at this additional visit:
  - A urine reagent strip, and urinalysis, urine culture and sensitivity test at the central laboratory will be collected.
  - If the investigators/subinvestigators judge that CIC should be initiated, then CIC should be initiated and managed according to the Guidance about the Management of PVR Urine Volume.
  - If CIC is not initiated and PVR continues to increase, the investigators/subinvestigators will determine whether the subject will be followed at regularly scheduled study visits or whether additional visits should occur.
- 4) If the PVR is decreasing or is unchanged then the subject will continue to be assessed per the schedule of visits and procedures

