#### Initiation of CIC

CIC should only be initiated when one of the following criteria is fulfilled:

- PVR is  $\geq 350 \text{ mL}$  at any post treatment visit, regardless of reports of associated symptoms by subjects; or
- PVR is  $\geq 200 \text{ mL}$  and  $< 350 \text{ mL}$  and the subject spontaneously reports associated symptoms (e.g., voiding difficulties and sensation of bladder fullness) that in the opinion of the investigators/subinvestigators require CIC.

The following will occur when initiating CIC:

- 1) CIC should be performed using sterile, single-use catheters.
- 2) An adverse event of urinary retention should be recorded.
- 3) A urine analysis with a urine reagent strip as well as urinalysis, urine culture and sensitivity test at the central laboratory should be performed. In addition, these tests and analyses will be performed at scheduled visits after CIC is initiated.
- 4) The subject should be seen at a follow-up visit 1 week later, when the results of PVR measurement, associated symptoms, and a urine analysis with a urine reagent strip are

reassessed while urinalysis, urine culture and sensitivity test are performed for reassessment at the central laboratory. The investigators/subinvestigators will determine whether the subject should then be followed at regularly scheduled study visits or whether additional visits should occur.

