## **Safety**

All AEs that occur during the study will be recorded and classified using the current Medical Dictionary for Regulatory Activities (MedDRA). Events will be summarized overall, by treatment cycle and for the first 12 week of 1st treatment phase ( $\leq 84$  days from 1st treatment). Frequencies of AEs will be presented by system organ class and preferred term. Summaries of treatment-related AEs (study drug-related and injection procedure-related), AEs leading to discontinuation, AEs by intensity, and SAEs also will be provided.

ANCOVA for change from baseline in PVR urine volume will be performed at each visit. This model will include the treatment group, site and a stratification factor as fixed factors, baseline PVR urine volume as a covariate. The proportion of patients who will have a change from baseline in PVR

category (urine volume of < 100 mL, ≥ 100 to < 200 mL, ≥ 200 to < 350 mL, and ≥ 350 mL) will be summarized by visit.

The proportion of subjects using CIC (for urinary retention or elevated PVR) post-treatment will be summarized by PVR category. Time to start of CIC from most recent treatment, duration of CIC and PVR volume at the time of initiation of CIC will be also presented.

The observed value of clinical laboratory test and its change from baseline will be summarized by treatment group. The number of subjects with values outside of normal range by visit will be tabulated by treatment group to evaluate the changes in clinical laboratory tests.

The observed value of vital signs and changes from baseline will be summarized by treatment group. Also the ECG findings by visit will be summarized by treatment group.

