8. SAFETY ANALYSES

The safety analyses will be based on the “Safety” population, unless otherwise specified. In detail, each Safety population will be used for each study phase as below table. In principle, summaries for TC1 will be only by treatment group, and summaries for GTC1, GTC2, GTC3 and Overall will be by treatment group and its total.

For AEs:

Study phase	Population	Summary Group
TC1	SPDB	By treatment group
GTC1	SP1	By treatment group and total
GTC2	SP2	By treatment group and total
GTC3	SP3	By treatment group and total
Overall	SP1	By treatment group and total

NOTES:

- The definition of population is described in [Analysis Populations](#).

For other than AEs:

Study phase	Population	Summary Group
TC1	SPDB	By treatment group
GTC1, GTC2, GTC3	SP1	By treatment group and total

NOTES:

- The definition of population is described in [Analysis Populations](#).

Safety data from unscheduled visit will not be included in safety analysis (but included in listing), and safety data at last visit will be treated as Study Exit in safety analyses (but treated as Withdrawal in listing).

Visit displayed in safety analyses will be summarized below table for study phases and endpoints. SPDB (for TC1) and SP1 (for GTC1, GTC2 and GTC3) will be used for these summaries. Separate displays will be provided for TC1 and for GTCs (GTC1, GTC2 and GTC3).

Endpoints	Study phase	Study visit displayed in safety analyses table
Vital Sign	TC1	Baseline, Week 2, Week 6, Week 12, Week 18, Week 24, Week 30, Week 36, Week42, Study exit
	GTC1	Study baseline, Qualification for GTC1 [1], Week 0 [1], Week 2, Week 6, Week 12, Week 18, Week 24, Week 30, Week 36, Week42, Study exit
	GTC2	Qualification for GTC2, Week 0, Week 2, Week 6, Week 12, Week 18, Week 24, Week 30, Study exit
	GTC3	Qualification for GTC3, Week 0, Week 2, Week 6, Week 12, Week 18, Study exit
Clinical laboratory (chemistry and hematology), ECG	TC1	Baseline, Week 12, Study exit
	GTC1	Study baseline, Qualification for GTC1 [1], Week 12, Study exit

CONFIDENTIAL

204947

Endpoints	Study phase	Study visit displayed in safety analyses table
	GTC2	Qualification for GTC2, Week 12, Study exit
	GTC3	Qualification for GTC3, Week 12, Study exit
Body Weight	TC1	Baseline, Study exit
	GTC1	Study baseline, Qualification for GTC1 [1], Study exit
	GTC2	Qualification for GTC2, Study exit
	GTC3	Qualification for GTC3, Study exit
PVR	TC1	Baseline, Week 2, Week 6, Week 12, Week 18, Week 24, Week 30, Week 36, Week42, Study exit

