3.110.	SP1	LB1	Summary of Hematology Changes From Baseline: GTCs	ICH E3.		Y
3.111.	SPDB	LB3	Summary of Shift from Baseline with Relative to Normal Range in Hematology: TC1	ICH E3	Y	Y
3.112.	SP1	LB3	Summary of Shift from Baseline with Relative to Normal Range in Hematology: GTCs	ICH E3		Y
Laboratory: Urinalysis						
3.113.	SPDB	UR1	Summary of Worst Case Urinalysis Results (Discrete or Character Values) Post-Baseline Relative to Baseline: TC1	ICH E3	Y	Y
3.114.	SP1	UR1	Summary of Worst Case Urinalysis Results (Discrete or Character Values) Post-Baseline Relative to Baseline: GTCs	ICH E3		Y
Laboratory: Hepatobiliary (Liver)						
3.115.	SP1	LIVER10	Summary of Hepatobiliary Laboratory Abnormalities	IDSL	Y	Y
ECG						
3.116.	SPDB	EG1	Summary of ECG Findings: TC1	IDSL	Y	Y
3.117.	SP1	EG1	Summary of ECG Findings: GTCs	IDSL		Y
Vital Signs						
3.118.	SPDB	VS1	Summary of Vital Signs Data by Visit: TC1		Y	Y
3.119.	SP1	VS1	Summary of Vital Signs Data by Visit: GTCs			Y

CONFIDENTIAL

204947

Safety : Tables						
No.	Population	IDSL / TST ID / Example Shell	Title	Programming Notes	Report at Interim	Report at Final
3.120.	SPDB	VS1	Summary of Change From Baseline in Vital Signs by Visit: TC1	ICH E3	Y	Y
3.121.	SP1	VS1	Summary of Change From Baseline in Vital Signs by Visit: GTCs	ICH E3		Y
Post Void Residual (PVR) urine volume						
3.122.	SPDB	Study specific	Summary of PVR urine volume:TC1		Y	Y
3.123.	SP1	Study specific	Summary of PVR urine volume: GTCs			Y
3.124.	SPDB	Study specific	Summary of Change from Baseline in PVR urine volume:TC1		Y	Y
3.125.	SP1	Study specific	Summary of Change from Baseline in PVR urine volume: GTCs			Y
3.126.	SPDB	Study specific	Summary of ANCOVA for Change from Baseline in PVR urine volume in TC1		Y	Y
3.127.	SPDB	Study specific	Number and Percentage of Subjects with PVR urine volume category: TC1		Y	Y
3.128.	SP1	Study specific	Number and Percentage of Subjects with PVR urine volume category: GTCs			Y
3.129.	SPDB	Study specific	Summary of PVR urine volume at initiating CIC		Y	Y
3.130.	SPDB	Study specific	Summary of PVR urine volume:TC1 by Age		Y	Y
3.131.	SPDB	Study specific	Summary of Change from Baseline in PVR urine volume:TC1 by Age		Y	Y
3.144	SPDB	Study specific	Number and Percentage of Subjects with PVR urine volume category (Change from Baseline): TC1		Y	Y

CONFIDENTIAL

204947

Safety : Tables						
No.	Population	IDSL / TST ID / Example Shell	Title	Programming Notes	Report at Interim	Report at Final

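### The SAP's listing flag for PVR at the start of catheterisation marks every value 14 or more days old and omits those 1 to 13 days old; the related table's fallback is undefined

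*SAP*

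**What the plan says.** SAP 8.5.1 holds two rules for the PVR at the start of CIC.

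- **Listing flag.** The PVR listing (Listing 35 in the amended SAP, 11.10.11) has a column set as follows: "Yes, if the date of PVR is on or at least 2 weeks (14 days) prior to the start date of CIC". The rule does not reserve older values for cases without a same-day PVR, sets no earliest date and does not select a single record.
- **Summary table.** Table 3.129, "Summary of PVR urine volume at initiating CIC", uses the PVR at the time CIC starts, "or 2 weeks prior to CIC if not available at the time of initiation".

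Both rules read the same in the April 2018 SAP and in the July 2018 amendment. Appendix 12, added by the amendment, settles which reasons for catheterisation count in each output. It does not deal with dates.

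Protocol 9.4.2 (Safety) states the aim: "PVR volume at the time of initiation of CIC will be also presented". SAP sections 8 and 11.5.2 keep data from unscheduled visits in listings but leave them out of summaries.

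**The concern.** A flag for the value at CIC initiation should mark the same-day PVR or, failing that, the nearest earlier one. This rule rejects the nearest earlier values and accepts all remote ones. The most natural explanation is that a look-back of up to two weeks was meant and that the words for a minimum were written in place of those for a maximum.

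Two outputs are exposed. In the listing, one CIC start can carry several flagged values, including one from before injection. Exclusion criterion 22 caps the screening PVR at 100 mL, while protocol 7.4.7 starts CIC at 350 mL, or at 200 mL with symptoms. A flagged screening value could therefore be misread as CIC started below the protocol threshold. In Table 3.129 the fallback is not precise enough to program. The flag is the only place in 8.5.1 where the two weeks are written out in days, so a programmer could reasonably reuse it. The table is produced at both the interim and the final analysis, and the interim serves a regulatory submission.

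**Working it through.** The plan states no figure to reproduce, so the check applies the flag rule to the visit schedule.

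**Inputs**
- PVR visits in treatment cycle 1 (SAP 8): "Baseline, Week 2, Week 6, Week 12, Week 18, Week 24, Week 30, Week 36, Week42, Study exit". Target days (SAP 11.3): Week 2 = Day 15, Week 6 = Day 43, Week 12 = Day 85.
- Baseline PVR (protocol Table 1, footnote f): "Could be performed during the screening phase excluding diary data collection days". The screening phase is within 28 days before injection.
- Assumed, because the documents give no CIC start dates: CIC start days and a screening PVR on Day -7.

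**Formula.** The gap is (CIC start day) - (PVR day) after injection. For a screening PVR on Day -k it is (CIC start day) - 1 + k, because there is no Day 0. The literal flag is Yes if the gap is 0, or 14 or more. The comparison rule takes the same-day value or, if none, the latest post-injection value 1 to 14 days old.

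| CIC start | PVR record | Gap (days) | Literal flag | Comparison rule |
|---|---|---|---|---|
| Day 22, no same-day PVR | Screening, Day -7 | 22 - 1 + 7 = 28 | Yes | No |
| | Week 2, Day 15 | 22 - 15 = 7 | No | Yes |
| Day 43, at the Week 6 visit | Screening, Day -7 | 43 - 1 + 7 = 49 | Yes | No |
| | Week 2, Day 15 | 43 - 15 = 28 | Yes | No |
| | Week 6, Day 43 | 0 | Yes | Yes |
| Day 50, no same-day PVR | Screening, Day -7 | 50 - 1 + 7 = 56 | Yes | No |
| | Week 2, Day 15 | 50 - 15 = 35 | Yes | No |
| | Week 6, Day 43 | 50 - 43 = 7 | No | Yes |

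**Reach of the omission.** Over CIC start days 1 to 84, a scheduled post-injection PVR is 1 to 13 days old on Days 16-28 (13 days) and Days 44-56 (13 days). That is 26 of 84 possible start days. It counts days and does not estimate the share of subjects.

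**When screening is the only flagged value.** Without a same-day PVR this holds up to Day 15 + 13 = Day 28. With the Week 2 visit on Day 12 or Day 18 the limit is Day 25 or Day 31. For very early CIC nothing is flagged: before Day 8 if screening was on Day -7 (8 - 1 + 7 = 14), and before Day 14 if it was on Day -1 (14 - 1 + 1 = 14).

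**The table's fallback.** Under protocol 7.4.7, after a PVR of 200 to <350 mL that does not lead to CIC, "the subject will be seen at an additional visit 1 week later, when the PVR and any associated symptoms will be reassessed". If CIC starts at that recheck, the recheck PVR has gap 0 and the preceding one has gap 7. If the recheck is classed as an unscheduled visit, SAP section 8 removes its PVR from analyses and Table 3.129 needs the fallback. The 7-day-old value then qualifies under a within-14-days reading. It fails under an exactly-14 or at-least-14 reading. The SAP does not choose between them.

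**The case against.** The strongest reply is that a same-day PVR is the normal case. Protocol 7.4.7 says "CIC should only be initiated when one of the following criteria is fulfilled", and both criteria rest on a measured PVR. The one-week recheck measures it again. The flag does mark same-day values. This stands and narrows the problem, but it does not remove it: as the Day 43 rows show, older records are flagged beside the same-day one.

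It is also fair to say that Table 3.129 has its own rule, with the same-day value first, and that this rule does not use the flag's minimum. That stands too. For the table, only the ambiguity of the fallback and the status of unscheduled visits remain.

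Three stronger readings are tempting, and the documents do not support them.

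- *The reported values are often pre-injection.* The documents give no CIC start dates, so no frequency can be stated. The illustration in SAP 8.5.2 concerns CIC duration and contains no PVR data.
- *The listing hides the recent value.* It shows the date, study day and result of each PVR, and unscheduled readings are kept. The recent value is visible and merely lacks a Yes.
- *Each affected subject is wrong by at least 100 mL, enough to shift the mean in Table 3.129.* The 100 mL is the distance from the entry limit of 100 mL to the lower CIC threshold of 200 mL. It applies only if a screening value replaces the true one, and nothing in the table's rule sends a screening value there. An older flagged value may also be post-injection and of any size, as on Day 50.

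Other displays limit misreading: CIC use by maximum PVR category (Table 3.134), PVR categories by visit, and the CIC listing with dates and reasons.

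**Conclusion.** Wrong as written, and minor. The literal flag contradicts its own label and the protocol's stated aim, and nothing elsewhere in the SAP corrects it. The table's fallback is ambiguous rather than wrong. The effect is limited to Listing 35 and possibly to fallback values in Table 3.129. Both are descriptive safety outputs, and no hypothesis test, efficacy estimate or aspect of trial conduct depends on them.

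The size of the effect cannot be derived. It depends on when CIC started, on how often a same-day PVR was missing or excluded as unscheduled, and on how the fallback was programmed. The conclusion on the flag assumes only that its words are applied literally. The conclusion on the table assumes only that a programmer must give the two-week fallback some definite meaning.

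**What to change.** Replace both sentences in SAP 8.5.1 with one definition, used for Table 3.129 and for the listing flag: *the PVR dated on the CIC start date; if none, the latest post-injection PVR dated within the 14 days before it; if none, missing; one record per CIC start.* State in the same place whether PVRs from unscheduled or additional visits count for this table, as an explicit exception to section 8 if they do.

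With this wording the Day 22 example selects the Week 2 value and the Day 43 example selects only the Week 6 value.

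The cost is a sentence or two in the SAP and a small change in program logic. The PVR and CIC dates are already collected, and no clinical rule changes.

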8.5.2. Clean Intermittent Catheterization (CIC)

Proportion of subjects who had used CIC at least once after the first treatment will be summarized by treatment group (and total for GTC1, GTC2, GTC3 and Overall) and study phases (TC1, GTC1, GTC2 and GTC3). As described in 8.5.1, only data of use of CIC with the reason for urinary retention or elevated PVR will be used for any analyses.

Proportion of subjects initiating CIC by raw PVR urine volume category of maximum PVR volume in TC1 will be summarized by treatment group. This summary is only for TC1. The category is described in 8.5.1.

[figure not shown]
Duration of using CIC will be summarized by treatment group (and total for GTC1, GTC2, GTC3 and Overall) and study phases (TC1, GTC1, GTC2 and GTC3) and listed. This listing includes the CIC with the reason for urinary retention or elevated PVR not include CIC with reason for “other”. Duration of using CIC is calculated cumulatively as

(Duration of using CIC in a given TC) = Sum of {(Date of A) – (later of “start date of CIC” or “date of the study drug treatment in this TC if not initiating CIC at this TC”) + 1}

- (For CIC not using at date of study complete or withdrawal) *Date of A = (earlier of “stop date of CIC” or “the day before the day of the study drug treatment for next TC if using CIC at re-treatment”)*
- (For CIC using at date of study complete or withdrawal) *Date of A = (later of “stop date of CIC” or “date of study complete or withdrawal”)*

In this calculation, if a given subject use CIC across next study drug treatment, the day of study drug treatment will be regarded as the use of CIC in next TC.

Below figure is to illustrate the example of duration of using CIC calculation.

In this example, this subject had CIC five times. In the calculation of each duration of using CIC in TC1,

- Duration of CIC 1st; day 9 – day 3 + 1 = 7
- Duration of CIC 2nd; day 22 – day 20 + 1 = 3
- Duration of CIC 3rd in TC1; (day 85 -1) – day 80 + 1 = 5

As result, duration of using CIC in TC1 is 7 + 3 + 5 = 15 days.

CONFIDENTIAL

204947

In the calculation of each duration of using CIC in TC2,

- Duration of CIC 3rd in TC2; day 91 – day 85 +1 = 7
- Duration of CIC 4th; day 203 -day 201 +1 = 3
- Duration of CIC 5th; day 225 – day 211 + 1 = 15

As result, duration of using CIC in TC2 is $7 + 3 + 15 = 25$ days.

Time to onset of first CIC will be summarized in TC1 analysed according to “Study Specific Safety Analyses for Time to Event data” below table.

(Time to onset of first CIC) = (The date of using CIC first in TC1) – (the date of first treatment) + 1

Listing of CIC data will be produced. This listing will include the following items.

- Site ID, Subject ID, Treatment group, Start date of CIC / End date of CIC, Duration of CIC, Time to onset of first CIC in TC1, Reason for catheterization (urinary retention, elevated PVR or other)

Study Specific Safety Analyses for Time to Event data	
Endpoint(s)	

 ● Time to onset of first CIC (section 8.5.2) ● Time to onset of UTI (section 8.5.3) ● Time to onset of Urinary retention (section 8.5.4) 	
Model Specification	

 ● Cox proportional hazard model will be used for estimating hazard ratio and its 95% confidence interval. This Cox model include treatment and a stratification factor as fixed effect. 	
Model Results Presentation	

 ● The p-values will not be calculated because p-value is not of interest for safety endpoint in this study. ● The hazard ratio to placebo and its 95% confidence interval will be estimated. 	
Censoring	

 ● If the subject withdraws the study prematurely before receiving 2nd treatment, this subject will be regarded as censored at the date of study withdraw. ● If the subject receives 2nd treatment without any event of interest (i.e., first CIC, UTI or Urinary retention) in TC1, this subject will be regarded as censored at the date of receiving 2nd treatment. 	

